12.8 Protocol Adherence

The Investigator (s) agree to conduct the study in accordance with this protocol. Prior to beginning the study, the Investigator (s) must sign the protocol signature page.

An Investigator must not make any changes in a study without first receiving approval from the Sponsor and IRB/EC, except when necessary to eliminate apparent immediate hazards to a Subject.

With the exception of emergency situations, no deviations to this CIP will be permitted. In the event of an emergency situation, the Principal Investigator must notify their DePuy Synthes clinical operations contact immediately. A full written report of the situation must be forwarded to the IRB/EC who approved the original CIP and DePuy Synthes Joint Reconstruction within 10 working days of the event.

12.9 CIP Amendments

If it becomes necessary to amend the Clinical Investigation then the nature of the amendment will be agreed between the Sponsor and the Principal Investigator(s) and this will be recorded with a justification for the amendment. The appropriate IRB/EC, will be informed of any amendments.

12.10 Investigator Reporting Responsibilities

In fulfillment of study related requirements, the Investigator is responsible for preparing and submitting complete, accurate, and timely reports as described below.

Table 12-1: Investigator Reporting Responsibilities

Report	Description	Action
Withdrawal of IRB/EC approval	The Investigator will promptly notify the Sponsor of a withdrawal of approval by the reviewing IRB/EC or of the Investigator's part in an investigation within 2 weeks.	Preferably within 2 weeks
Progress Report	If required by your IRB/EC, the Investigator is responsible for submitting progress reports on the investigation to the reviewing IRB/EC.	As required per your IRB/EC
Reports of deviations from the investigational plan	The Investigator will notify the Sponsor of any deviation from the Investigational Plan as soon as able. The Investigator will notify the IRB/EC of any deviation from the Investigational Plan per the IRB/EC requirements.	Per IRB/EC requirements; at least annually
Other	The Investigator will, upon request of a reviewing IRB/EC or Sponsor, provide accurate, complete, and current information about any aspect of the investigation.	As requested

The Principal Investigator may delegate a qualified associate(s) to complete one or more of the above functions. However, the Principal Investigator retains the overall responsibility for Subject safety, proper conduct of the study including obtaining Subject Informed Consent, compliance with this study plan, and the collection of all required data.

12.11 Investigator Site File

Each Investigator and all personnel from the investigational site must maintain accurate, complete, and current information about all aspects of this Clinical Investigation. This includes documentation relating to the Investigator's participation, Subject information and correspondence: electronic, written, and verbal, relating to any aspect of the clinical investigation.

The records are maintained in the Investigator Site File consisting of, but not limited to, correspondence with other participating Investigators, the reviewing IRB/ EC, and the Sponsor.

Upon receipt of copies of changes or revision updates to the Clinical Investigation Plan (otherwise known as the Study Protocol) from the Sponsor, the Investigator will add the updated document and Revision Log to the Investigator File. The outdated version will be filed.

12.12 Regulatory Requirements

This clinical investigation is a post-marketing surveillance study to obtain additional data. The devices are FDA cleared/approved and CE marked products cleared for sale by the appropriate regulatory authority in the country(ies) in which this clinical investigation is to be conducted.

12.13 Investigator Study Termination

The Investigator may prematurely terminate the clinical investigation at any time. Should this be necessary, the procedures will be arranged on an individual clinical investigation basis after review and consultation by both parties. In terminating the clinical investigation, the Sponsor and the Investigator will assure that adequate consideration is given to the protection of the Subject's interests, all documentation is archived per Section 12.5 and the appropriate bodies such as the IRB/EC are informed as appropriate.

13 SPONSOR OBLIGATIONS

13.1 IRB/EC Approval

The Sponsor requires this Clinical Investigation Plan to be submitted to the IRB/EC for initial review and approval before implementation at each site. Additionally, all protocol amendments must be submitted to the IRB/EC for review and approval before implementation.

Each site is required to submit a copy of the IRB/EC initial approval. Additionally, US sites are required to submit a copy of the IRB renewal(s), typically annually, to the Sponsor for filing in the study's Trial Master File. The site is to maintain the original documentation of the initial approval and annual renewals in the site's Investigator Site File.

13.2 Investigator Training, Pre-Investigational Visit

Prior to enrolling Subjects in this study, the Investigator and/or appropriate site personnel will be trained on the study protocol to include:

- the general aspects of study administration,
- all procedures in the protocol, and
- the procedure for e-data acquisition and transmission.

The Sponsor will be offering hands on training to supplement professional education of the surgeon on the implant and surgical instruments, as needed.

13.3 Study Monitoring

Sponsor oversight will be maintained per Sponsor policies and procedures. On site monitoring will be done at the discretion of the Sponsor. Should a monitoring visit be required, the Sponsor will work with the site to determine the date(s).

During the visit, the Sponsor and authorized Sponsor representatives shall be given access to all study records, to include study Subject medical records.

All study Subjects are required to sign the Informed Consent Document allowing access to and release of their personal health information.

13.4 Labeling

Refer to Exhibit D for Product Labeling.

13.5 Sponsor Study Termination

The Sponsor may prematurely terminate or suspend the clinical investigation as a whole or at an individual investigational site for significant and documented reasons. Reasons for premature termination or suspension include, but are not limited to safety, inadequate recruitment, Principal Investigator issues, device related problems, alignment with business strategy or administrative issues.

In the event of the study being terminated, any enrolled Subjects that have not yet had the surgical procedure would be treated as per their surgeon's standard practice using implants and instruments of the surgeon's choice. All enrolled Subjects who have received an ATTUNE implant within the study would continue to be cared for by their surgeon according to his/her standard of care. No further study-related procedures or data collection would occur.

13.6 Sponsor Reporting Responsibilities

The Sponsor is responsible for preparing and submitting complete, accurate and timely reports per Section 9.6.3.

13.7 Financial Agreement

Funding of the clinical investigation will be detailed in a separate agreement between the Sponsor and the Institution where the clinical investigation is being conducted and the Principal Investigator (where permitted by the Institution).

13.8 Publication Policy and Public Disclosure

The Sponsor is committed to publication of this study. A multi-center publication will be completed prior to allowing individual sites to publish their own data. Authorship decisions will be aligned with the International Committee of Medical Journal Editors^F. All manuscripts including data from this study will be reviewed and approved by the Sponsor, and each author, prior to any submission. All authors must disclose financial or personal affiliations that could be considered conflicts of interest.

The sponsor will register this study on www.clinicaltrials.gov per FDAAA regulations.

13.9 Insurance

The Sponsor will secure and maintain in full force and effect, throughout the duration of the Clinical Investigation, clinical trial insurance in line with national regulations. The type of insurance for each participating site is detailed within the respective Clinical Trial Agreement or equivalent which will be executed before the start of Subject recruitment at that site.

^F <http://www.icmje.org/>

15 CLINICAL INVESTIGATIONAL PLAN EXHIBITS

Exhibit	Description of Exhibit
A	Sample Case Report Forms
B	Surgical Technique
C	Implant Product Codes
D	Instructions for Use (IFU)
E	Adverse Events: Tips & Pearls 
• Listing of Non-reportable Adverse Events• Preferred Terms for Select TKA Related Adverse Events• Flowchart for AE reporting
F	Radiographic Protocol

## List of Abbreviations

AE	Adverse Event
AP	Anteroposterior
CI	Confidence Interval
CIP	Clinical Investigational Plan
CR	Cruciate Retaining
FB	Fixed Bearing
FM	Distal Femoral Varus-valgus
HKA	Hip-Knee-Ankle
MedDRA	Medical Dictionary for Regulatory Activities
OR	Operating Room
PS	Posterior Stabilizing
RP	Rotating Platform
RUI	Reusable Instrumentation
SAP	Statistical Analysis Plan
SD	Standard Deviation
SUI	Single-use Instrumentation
TKA	Total Knee Arthroplasty
TM	Proximal Tibial Varus-valgus

# 1 Study Design

This study is designed as a prospective, comparative, sequential, non-randomized, multi-center, controlled clinical investigation. Randomization will not be utilized in this study in order to isolate and learn if there are changes in Operating Room (OR) efficiency with Single-Use Instrumentation under normal operating room procedures.

There will be 4 centers worldwide that will recruit a total of 88 Subjects: 44 treatment [Single-Use Instrumentation, (SUI)] and 44 control [Reusable Instrumentation, (RUI)]. A complete description of the methods for determining sample size is contained in Section [7](#). The recruitment goal will be to evenly distribute enrollment across the four sites; therefore, it is expected that each site will enroll 22 Subjects (11 Control followed sequentially by 11 Treatment Subjects).

- The **Control group** will consist of 44 Subjects, 11 per site and the surgical procedure for these Subjects will be performed using Reusable Instruments (RUI).
- The **Treatment group** will consist of 44 Subjects, 11 per site and the surgical procedure for these Subjects will be performed using Single Use Instruments (SUI).

For a given site, either Cruciate Retaining (CR) or Posterior Stabilizing (PS) configurations will be used; consistent with their standard of care. Within a given CR site, the Investigator may choose to implant either the CR Fixed Bearing (FB) or CR Rotating Platform (RP) configurations. Similarly, within a given PS site, the Investigator may choose to implant either the PS FB or PS RP configurations.

One surgeon at each site will complete all RUI and SUI surgical cases including the learning curve cases. No Sub-Investigators will be permitted to perform surgery to avoid possible confounding issues with varying surgical process. All sites will have previously completed their learning curve cases with the ATTUNE Primary Implant implanted using RUI prior to enrolling the first patient. Then after the completion of all RUI study cases, a series of learning curve cases will be permitted for the use of SUI. The duration of the SUI learning curve is anticipated to be approximately 5 cases and is at the discretion of the Principal Investigator. These early cases that are within the learning curve will not be enrolled into this study at each site.

The study is designed to assess mechanical axis alignment, component alignment, safety, operating room efficiency and surgeon satisfaction achieved using the two instrumentation systems. The primary, secondary, and exploratory objectives are presented below.

### 1.1 **Primary Objective**

To determine whether the mechanical axis alignment achieved with SUI instrumentation is non-inferior to the alignment achieved with RUI instrumentation. Mechanical axis alignment is defined as the line drawn from the center of the femoral head through the center of the knee and ankle and will be measured from weight bearing long-leg (51") Anteroposterior (AP) radiographs, taken approximately 90 days post-op (when subject has reached full knee extension) and read by an independent radiographic reviewer.

### 1.2 **Secondary Objectives**

- To compare alignment achieved with SUI vs. RUI of individual components in the frontal and sagittal planes, specifically: distal femoral varus-valgus (FM), proximal tibial varus-valgus (TM), femoral component flexion and tibial slope.
- To compare the type and frequency of adverse events, from the time of surgery through to withdrawal of a subject or the end of the study (includes serious adverse events, and device and/or procedure-related adverse events), between the SUI and RUI instrument groups.

### 1.3 **Exploratory Objectives**

- To compare SUI and RUI operating room times from OR set-up through OR clean down as detailed in the Clinical Investigational Plan (CIP) Table 8-3.
- To determine whether SUI provides opportunity to reduce the incidence of minor procedural obstacles during the time in the OR.
- To compare Surgeon satisfaction of SUI instrumentation to RUI instrumentation.

## 2 Treatment Assignment

Treatment assignment is described in Section [1](#).

## 3 Randomization and Blinding Procedures

Neither randomization nor blinding will be implemented in this study.

## 4 Interval Windows

Data collected throughout the study will be assessed for compliance with the protocol-specified visit schedule. Three windows are defined based on the number of days prior to or after surgery, Day 0. Visits conducted within the intervals shown in Table 4-1 will be assessed for compliance with the protocol. If multiple visits fall into the same interval, the result closest to the target study day will be used in analysis. All safety data will be included in the Safety analysis.

**Table 4-1 Interval Windows**

STUDY VISIT	Target Study Day	Lower Bound Day	Upper Bound Day
Pre-Op	-90	-180	0
Surgery	0		0
Immediately Post-op	15	1	29
3 Month	90	30	150

## 5 Levels of Significance

Only the primary endpoint analysis in this study is prospectively powered and will be conducted with a 1-sided independent means t-test with an alpha of  $\alpha = 0.05$ . Confidence intervals and p-values may be provided for demographic or baseline comparisons, or for other secondary and tertiary endpoints, but these are all deemed to be exploratory. Unless otherwise stated, these confidence intervals will be 2-sided 95% confidence intervals. Because these endpoint analyses are deemed to be exploratory, there will be no adjustment of significance levels because of testing multiple hypotheses. No labeling claims will therefore be made based on these exploratory findings.

## 6 Analysis Sets

The determination of subjects to be excluded from the Per Protocol Set will be based on study team review of noncompliance and will be documented separately. The original CIP was written to exclude subjects who had a major protocol deviation, but such deviations may be about study compliance and not necessarily about the scientific integrity of the data. Analysis set definitions from the CIP and those slightly revised definitions per this SAP appear below.

### 6.1 CIP Analysis Set Definitions

**Consented/Enrolled Population:** All cases consented to participate in this study.

**Safety Population:** All cases that received the Attune device and the assigned instruments were used.

**Per Protocol Population:** All cases from the Safety Population that did not have major protocol violations.

### 6.2 Modified Analysis Set Definitions

**Consented/Enrolled Set:** All subjects who consented to participate in the study.

**Safety Set:** All subjects who received an ATTUNE device.

Note: If the treatment instrumentation used for the tibial and femoral cuts differ, the subject will be included in the instrumentation group used for the distal femoral cut. If both SUI and RUI were used for a single cut (tibial or femoral), the subject will be included in the first used instrumentation group. The Safety Set will be used to present results for Demographic, Exploratory Endpoints, and Adverse Events.

**Per Protocol Set:** All Safety Set subjects for whom a single instrumentation type was used and who had no protocol noncompliance evaluated which presents serious risk for the validity or integrity of the clinical trial data and/or regulatory acceptability of the sponsor/study/site; safety or well-being of the subject at risk. The Per Protocol Set will be used to present analyses of the primary and secondary endpoints.

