8.4.2 Intra-operative Withdrawal

The Investigator may withdraw the Subject intraoperatively for safety reasons, for example, it may become clear that the patient is not suited to receive the implant to be used for the study or the surgeon did not use the assigned instruments for whatever reason. Please refer to table 8-6 for further guidance.

Table 8-6: Intraoperative Withdrawal example

Intraoperative Withdrawal: Potential Subjects to be withdrawn from study participation intraoperatively.		
Example	Action	Follow Up
Intraoperatively determined to be ineligible (example, ATTUNE primary implant not suitable)	Update Screening/Enrollment Log as “Intraoperative Withdrawal” and document reason Submit Subject History, and End of Study/Withdrawal eCRFs to Sponsor Inform Subject that they were withdrawn	Do not continue
Example	Action	Follow-Up
Intraoperatively the assigned instruments are not used to perform the proximal tibia and/or distal femoral resections	Update Screening/Enrollment Log as “Intraoperative Withdrawal” and document reason Submit Subject History, Operative Details, Device Log and End of Study/Withdrawal eCRFs to Sponsor. Submit Adverse Event as applicable. Inform Subject that they were withdrawn	Do Not continue
Intraoperatively the ATTUNE implant is attempted but not retained	Update Screening/Enrollment Log as “Intraoperative Withdrawal” and document reason Submit Subject History, Operative Details, Device Log and End of Study/Withdrawal eCRFs to Sponsor. Submit Adverse Event as applicable. Inform Subject that they were withdrawn	Do Not continue

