8.4.3 Enrollment Replacement Rules

Since Subjects are enrolled at the time of consent, any Subject that is withdrawn preoperatively or intraoperatively prior to receiving the study implant will be replaced with subsequent Subjects. Overall, the number of Subjects who received an ATTUNE implant using a study device (with either the RUI or SUI instrumentation), across all sites must meet the sample size of 88.

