10.8 Analysis Sets

Below is a flow chart showing the analysis sets.

Figure 10-1: Analysis Populations Flowchart

The primary analysis dataset will be the Per Protocol population.

Adverse event comparisons will be conducted using the Safety population.

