10.10 Analysis Plan

The primary endpoint is a non-inferiority test of mean absolute mechanical axis angle, comparing single use and reusable instrument results with a non-inferiority margin of 1.5° using a 1-sided independent means t-test and $\alpha = 0.05$. The primary endpoint analysis null hypothesis will be rejected and non-inferiority will be concluded if the 1-sided upper 95% confidence limit for $\mu_{SUI} - \mu_{RUI}$ is less than 1.5°.

Preoperative demographics will be compared to determine whether differences exist between treatment groups. Age and BMI will be compared using two-tailed independent means t-tests. Gender distribution will be compared with a Fisher's exact test.

Secondary analyses include:

- Tests of differences for individual component alignment in the frontal and sagittal planes, specifically: distal femoral varus-valgus (FM), proximal tibial varus-valgus (TM), femoral component flexion and tibial slope using (independent means two-tailed t-tests).
- The types and frequencies of adverse events will be tabulated for all enrolled knees. The proportion of each complication will be compared using a Fisher's Exact Test (2 x 2 only) and Chi-square.

Exploratory analyses will be conducted to see if SUI improves OR efficiency compared to conventional (RUI) instruments. Exploratory analyses will also be conducted to investigate OR step times, inter-site differences in OR times, and issues that potentially introduced delays or interruptions in the surgical flow.

The Following Table presents a summary of the planned statistical tests:

Table 10-2: Planned statistical comparisons

Comparison	Purpose	Expected Result
Mean absolute mechanical axis non-inferiority	Primary efficacy	SUI Non-inferior to RUI
Demographic comparisons	Test comparability	No difference
Distal Femoral Varus-Valgus (FM)	Secondary efficacy	No difference
Proximal Tibial Varus-Valgus (TM)	Secondary efficacy	No difference
Femoral flexion	Secondary efficacy	No difference
Tibial slope	Secondary efficacy	No difference
OR Efficiency	Exploratory Analysis	No difference

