11 DEVICE DESCRIPTION

All products used in this CIP have the appropriate regulatory approval, FDA clearance/approval for commercial distribution and bear the CE mark. The ‘devices’ under study are the surgical instruments.

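### The Safety Set is defined by receipt of the implant rather than use of the instruments under study, so an exposed but unimplanted knee leaves the by-group adverse event comparison

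*SAP*

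**What the plan says.** **What is under study.** Protocol section 11 says that the devices "under study are the surgical instruments". Protocol 9.3 adds that the same implant is used with both types.

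**Who is in the Safety Set.** SAP 6.2 admits "All subjects who received an ATTUNE device". SAP 6.1 gives the definition from the clinical investigational plan (CIP): "All cases that received the Attune device and the assigned instruments were used". That version names the ATTUNE device and the instruments as separate conditions, so the device in these definitions is the implant. The SAP dropped the instrument condition and kept the implant condition. The note in SAP 6.2 on the distal femoral cut and the first-used instrument only assigns a group to a subject who is already in the set.

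**What the set is used for.** SAP 6.2: "The Safety Set will be used to present results for Demographic, Exploratory Endpoints, and Adverse Events". Protocol 10.8: "Adverse event comparisons will be conducted using the Safety population". Protocol 10.10, however, says: "The types and frequencies of adverse events will be tabulated for all enrolled knees". Enrolled means consented (protocol 5.3 and 8.2.1).

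**Intra-operative withdrawal.** The first row of protocol Table 8-6 covers a subject found ineligible during surgery, for example because the ATTUNE primary implant is not suitable. Its form instruction is "Submit Subject History, and End of Study/Withdrawal eCRFs to Sponsor Inform Subject that they were withdrawn". A later row covers an implant that was attempted but not retained. Follow-up stops in both cases. Protocol 8.4.3 then says that "any Subject that is withdrawn preoperatively or intraoperatively prior to receiving the study implant will be replaced with subsequent Subjects", so that 88 subjects in all receive an implant.

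**The concern.** In a comparison of instruments, exposure begins when an instrument is used on the knee. A safety set that also requires receipt of the implant depends on something that happens after exposure and may be affected by it. If an intra-operative problem leads the surgeon not to use the ATTUNE primary implant, the subject drops out of both numerator and denominator for the instrument group, and another subject takes the place.

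The secondary safety objective compares the type and frequency of adverse events between the instrument groups, including device-related and procedure-related events. Protocol 9.3 lists bone fracture, soft tissue damage and instrument breakage among the potential risks. With 44 subjects per group, one or two subjects more or fewer visibly change a percentage.

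**Working it through.** **Step 1: the plan's own figure.** Inputs from protocol 10.9 and SAP 7: margin 1.5°, SD 1.870°, one-sided alpha 0.05, 35 per group. The noncentrality is 1.5 / (1.87 × √(2/35)) = 3.36 on 68 degrees of freedom, and the noncentral t power is 95.3%, against 95% stated. Inflation for 20% loss gives 35 / 0.80 = 43.75, hence 44. Both figures reproduce. Nothing below changes them, since the point concerns membership of the safety set only.

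**Step 2: follow one knee through the rules.** Take a consented subject in whom a study instrument has been used and who is then found unsuitable for the implant.

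- Table 8-6, first row: withdrawn, not followed further.
- Protocol 8.4.3: replaced.
- SAP 6.2: no ATTUNE device received, so not in the Safety Set. The CIP version in SAP 6.1 gives the same result.
- SAP 6.2 and protocol 10.8: adverse events are presented and compared in that set, so the subject is in neither numerator nor denominator.
- SAP 8.5: all adverse events are listed, so a reported event remains visible outside the comparison.
- Protocol 10.10: adverse events are tabulated for all enrolled knees, so the subject is included.

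The fifth and sixth results do not restore the subject to the Safety Set, and the sixth contradicts the fourth. If the implant was attempted but not retained, the result cannot be determined, because the documents do not say whether that counts as received.

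**Step 3: how often this might arise.** The documents give no rate. If each operated subject has an assumed probability q of withdrawal after instrument use but before implantation, the chance of at least one among 44 is 1 − (1 − q)^44:

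| Assumed q | Chance of at least one in 44 |
|---|---|
| 1% | 36% |
| 2% | 59% |
| 5% | 90% |

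**Step 4: effect on the percentages.** Counts are assumed and limits are exact (Clopper-Pearson). If the exposed knee is kept and the arm is still filled to 44 implanted subjects, the denominator is 44 plus the kept knees.

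| Such knees, each with an event | Set defined by implant | Set defined by exposure |
|---|---|---|
| 1 | 0/44 (upper 97.5% limit 1 − 0.025^(1/44) = 8.0%) | 1/45 = 2.2% (0.06% to 11.8%) |
| 2 | 0/44 (same limit) | 2/46 = 4.3% (0.5% to 14.8%) |

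With two other subjects with events in each arm, the implant-based set shows 2/44 against 2/44 (Fisher p = 1.00). Two such SUI knees would make it 4/46 (8.7%) against 2/44 (4.5%), p = 0.68. The description changes; a test at this sample size would not.

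**The case against.** **Other text brings these subjects in.** Protocol 10.10 covers all enrolled knees, and SAP section 4 says that all safety data enter the safety analysis. The first is a real conflict and shows that exclusion is not a settled intention across the documents. The second stands in the section on visit windows and does not redefine the set. SAP 6.2, which names the set for adverse events, still excludes the subject.

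**The data are collected.** A reader might infer from the short form list in the first row of Table 8-6 that the operative record and the event would be lost. The documents do not support that. Table 8-3 requires the Operative Details and Device Log forms for all subjects and an Adverse Event form for any intra-operative complication. Protocol 9.7.1 sets reporting deadlines for serious events and for device-related or procedure-related events, apart from the non-reportable list. Table 8-6 is also headed as an example. The row needs harmonising; it is not a gap in capture.

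**The bias must favour SUI or hide a difference.** This too might be inferred and does not follow. The rule is the same in both arms. It would conceal an excess in whichever arm had more such cases, and no differential rate is given. Nor does the first row of Table 8-6 mention instrument failure or say that cuts had been made; an instrument-caused case is possible under that row but is not described there. Replacement subjects are implanted, which does not make them free of complications.

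**The comparison is exploratory.** SAP section 5 treats everything except the primary endpoint as exploratory and rules out labeling claims, SAP 8.5 plans a descriptive overview, and SAP 8.2 tabulates enrolled but untreated subjects and withdrawals. This limits the consequence. SAP 8.2 states no split by instrument group, however, so it does not supply the missing comparison.

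**Conclusion.** The point holds as a defect in the definition of the Safety Set and as an inconsistency between protocol 10.10 on one side and protocol 10.8 and SAP 6.2 on the other. As written, the rule omits from the by-group adverse event overview any subject exposed to a study instrument but not implanted, and leaves the attempted-but-not-retained case undefined.

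Its size is modest. The number affected is probably small, the event could still be found in the listing, and neither the primary analysis nor the sample size changes. One such knee with an event would move an arm from 0/44 to 1/45; that count is an assumption, not a figure from the documents. The direction of any bias is unknown. The change is worth making because it removes a selection effect from the safety comparison at almost no cost.

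**What to change.** - **SAP 6.2:** define the Safety Set as all subjects in whom any SUI or RUI study instrument was used at surgery, whether or not an ATTUNE implant was received or retained. Assign the group by the existing rule (distal femoral cut, or the first instrument used). Subjects withdrawn before any instrument use stay out.
- **Protocol 10.8 and 10.10:** use this one set for adverse event comparisons in both places.
- **Protocol 8.4.3:** let replacement fill the alignment sample, and state that a replaced subject who was exposed to study instruments remains in the Safety Set.
- **SAP 8.2 or 8.5:** tabulate by instrument group the knees in which the implant was not received or not retained.
- **Protocol Table 8-6, first row:** as a harmonising edit only, align the form list with Table 8-3.

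The cost is wording, one table row and one added tabulation; Table 8-3 already requires the forms. The downside is that safety denominators may slightly exceed 44 per group and differ from the number implanted, which a footnote can explain.
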